10.1 Investigator Records	
11. PUBLICATION	21
11.1CLINICAL TRIAL REGISTRATION11.2 PUBLICATION REVIEW	
I I.4 FUDLICATION INEVIEW	

Page 3 of 23

List of Abbreviations

ABI: Ankle Brachial Index

ACC/AHA: American College of Cardiology/American Heart Association

AE: Adverse Event

AEAC: Adverse Event Adjudication Committee

BA: Baloon angioplasty

CFR: Code of Federal Regulations

CLI: Critical Limb Ischemia CRF: Case Report Form

CSI: Cardiovascular Systems, Inc. DAS: Directional Atherectomy System

DCB: Drug coated balloon

DICOM: Digital Imaging and Communications in Medicine

DSMB: Data Safety Monitoring Board FDA: Food and Drug Administration

HIPAA: Health Insurance Portability and Accountability Act

ICF: Informed Consent Form

ICMJE: International Committee of Medical Journal Editors

IDE: Investigational Device Exemption

IRB: Institutional Review Board IVUS: Intravascular Ultrasound

NYU: New York University

OAD: Orbital Atherectomy Device OAS: Orbital Atherectomy System PAD: Peripheral Artery Disease

PI: Principal Investigator

QCA: Qualitative Comparative Analysis

QoL: Quality of Life

RGA: Returned Goods Authorization

SAE: Serious Adverse Event SFA: Superficial Femoral Artery

US: United States

VIAS: Video Image Analysis Software

Protocol Summary

Title	Directional versus Orbital Atherectomy plaque modification and luminal area assessment of the femoro-popliteal artery Via Intravascular Ultrasound
Short Title	DIRECT TRIAL
	A single center prospective, randomized study will be conducted to investigate plaque removal and luminal gain using CSI's DIAMONDBACK 360® Peripheral Orbital Atherectomy System (OAS) (St.Paul, MN) versus Medtronic's Hawkone Directional Atherectomy system (DAS) (Minneapolis, MN) assessed by angiography and Intravascular Ultrasound (IVUS) in patients diagnosed with symptomatic obstructive femoro-popliteal disease will be analyzed.
Brief Summary	Subjects will be randomized in a 1:1 fashion to receive treatment with either OAS (using CSI device) followed by Inpact Admiral drug coated balloon (DCB) or DAS (using the Hawkone device) followed by DCB. Subjects in both arms will undergo IVUS before and after atherectomy, as well as at the conclusion of the procedure.
	Clinical data will be collected at baseline, immediately prior to the procedure, during and immediately after the procedures, and within 30 days, 6 and 12 months office visits after the procedure. Data may also be collected at office or hospital visits that are not scheduled but occur up to 12 months after the procedure, if they pertain to treatment related to the obstructive femoro-popliteal disease. Data to be collected for this study includes demographics, medical history, procedural parameters and follow-up.
	The study will be conducted at one study center, 60 subjects will be accrued in the trial with 30 patients enrolled in the OAS arm and 30 patients enrolled in the DAS arm.

Version 23JUL2020 Page 5 of 23

Objectives	To investigate the hard and soft plaque removal with directional and orbital atherectomy by analyzing changes in plaque volume and composition and vessel size using intravascular ultrasound (IVUS). Freedom from complications, target vessel patency and target lesion revascularization (TLR) at 6 months and one year will also be evaluated.
	Primary Endpoint:
	Acute luminal gain (increase in minimal luminal area via IVUS measurement immediately following atherectomy)
	Secondary Endpoints:
Endpoint	-Plaque burden reduction. The plaque composition and amount of removed plaque will be analyzed via IVUSDevice success (≤ 30% residual stenosis following atherectomy, as measured by angiography, without adjunctive endovascular interventions) -Rate of procedural angiographic complications such as dissection, perforation, emboli, abrupt closure, need for bail out stentingMajor Adverse Event Rate at 30 days post procedure defined as clinical TLR, major unplanned amputation of the treated limb, or all-cause mortality -Rate of clinical TLR, unplanned amputation of the treated limb, or all-cause mortality at 6 and 12months post index treatmentPrimary patency at 1 year defined as freedom from target lesion restenosis detected with duplex ultrasound Peak Systolic Velocity Ratio (PSVR) is ≤ 2.4 -Rate of Hemodynamic Improvement as assessed by changes in ABI at 6 and 12 months as compared to post-procedural baseline (i.e., within 30 days)Improvement in Rutherford Clinical Category within 30 days, at 6 months and at 12 months, defined as an improvement in clinical status indicated by a decrease of one or more in Rutherford Clinical Category compared to baseline, that is attributable to the treated limb (in cases of bilateral disease).

Version 23JUL2020 Page 6 of 23

Study Duration	The duration of the study is expected to be approximately 2 years from the date of first enrollment (1 year for enrollment of approximately 100 subjects and a year for follow-up of 60 accrued subjects).		
Participant Duration	It will take 12 month for each individual participant to complete all participant visits.		
Population	The patients with obstructive superficial femoral or popliteal arteries disease as the main reason for their symptoms will be enrolled in this study.		
Study Sites	NYU Langone Health		
Number of participants	Number of participants projected for the entire study 100		
Description of Study Procedure	All subjects will undergo percutaneous revascularization of the femoro-popliteal arteries using a DAS or OAS device and balloon angioplasty as per the randomization arm. All patients will undergo at least 3 runs of IVUS: • a pre-treatment run to assess the severity and morphology of the plaque composition • a post-atherectomy run to assess changes post atherectomy treatment • a post drug coated balloon angioplasty (followed atherectomy) to assess changes in overall volumes.		
Statistical Analysis	The sample size for the study is not based on any statistical hypothesis. The mean differences between pre-procedure and post-procedure measures will be analyzed using paired t-tests. A p-value of ≤ 0.05 will be considered to indicate statistical significance. Descriptive statistics will be generated to describe study findings (i.e. subject demographics, plaque volume, lumen volume, vessel size, etc.).		

1. Key Roles

Version 23JUL2020 Page 7 of 23

Investigator:

[name], PhD, FACC [name] [contact] [contact]

Co-Investigators:

TBD

Center:

NYU Langone Health [name]

2. Introduction

2.1 Regulatory Classification

The sponsor has determined that this study is a medical device study which involves products currently on the market in the USA and these products have received clearance for use by the Food and Drug Administration (FDA). The clinical study requires the medical devices to be used in accordance with its FDA-cleared labeling. Therefore, it is a study which is exempt from the investigational device exemption (IDE) regulations of the FDA. There are no investigational products or procedures used in this study.

2.2 Study Description

A single center prospective, randomized study will be conducted to investigate plaque removal and luminal gain using CSI's DIAMONDBACK 360® Peripheral Orbital Atherectomy System (OAS) (St.Paul, MN) versus Medtronic's Hawkone Directional Atherectomy system (DAS) (Minneapolis, MN) assessed by angiography and Intravascular Ultrasound (IVUS) in patients diagnosed with symptomatic obstructive femoro-popliteal disease will be analyzed.

Subjects will be randomized in a 1:1 fashion to receive treatment with either OAS (using CSI device) followed by Inpact Admiral drug coated balloon (DCB) or DAS (using the Hawkone device) followed by DCB. Subjects in both arms will undergo IVUS before and after atherectomy, as well as at the conclusion of the procedure.

Clinical data will be collected at baseline, immediately prior to the procedure, during and immediately after the procedures, and within 30 days, 6 and 12 months office visits after the procedure. Data may also be collected at office or hospital visits which are not scheduled but may occur up to 12 months after the procedure, if they pertain to treatment related to the obstructive femoro-popliteal disease. Data to be collected for this study includes demographics, medical history, procedural parameters and follow-up.

The study will be conducted at one study center, 100 subjects will be enrolled, with 60 subject accrued in the trial: 30 patients randomized to the OAS arm and 30 patients randomized to the

Version 23JUL2020 Page 8 of 23

DAS arm. The duration of the study is expected to be approximately 2 years from the date of first enrollment (1 year for enrollment of 60 subjects and a year for follow-up).

2.3 Study Background and Justification

Peripheral arterial disease (PAD) of the lower extremities has an incidence and prevalence equal to that of coronary artery disease and is a major cause of morbidity and mortality. Endovascular treatment of femoral-popliteal lesion in patients with symptomatic PAD has been shown to improve exercise capacity and quality of life¹. Heavy plaque burden calcification is one of the most important predictors of unsuccessful angioplasty and poor short and long term procedural outcomes. Fitzgerald et al.² demonstrated that 74% of dissections after balloon angioplasty occurred in lesions with significant calcification.

Percutaneous removal of atherosclerotic material using atherectomy devices reduces the complications of traditional angioplasty such as dissection, elastic recoil and disruption of the internal elastic lamina of the artery. Directional and orbital atherectomy are two of the most common atherectomy approaches used to treat lower extremity PAD.

Directional atherectomy devices such as the Hawkone, Turbohawk and Silverhawk use a side cutting steerable blade that also has a distal nosecone to capture debris. The directional cutting design allows for extensive removal of calcific debris from the entire lumen while minimizing the direct trauma to the true intima. The Definitive LE study was an 800 patient prospective registry that demonstrated the safety and effectiveness of DAS in infrainguinal PAD. Primary patency rates were >90% after 6 months in both the claudicant and critical limb ischemia(CLI) groups.³ Smaller randomized trials of directional atherectomy vs traditional balloon angioplasty have demonstrated superior outcomes with directional atherectomy especially when treating long calcified lesions⁴.

Orbital atherectomy devices such as the Diamondback 360 use a diamond coated eccentrically mounted burr that spins in an orbit and increases in size at higher revolutions. This technique causes preferential sanding of the calcified plaque and a fixed luminal gain and can be used in vessel ranging from 2mm-7mm in diameter. IVUS analysis of lesions treated with orbital atherectomy significant lesion modification by modifying the calcified component of the plaque burden.⁵ The Compliance 360 trial randomized 65 patients to either balloon angioplasty (BA) or OAS and BA. This trial showed that compared to BA alone, OAS+ BA yields better luminal gain and decreases incidence of adjunctive stenting.⁶ Similarly, the Calcium 360 randomized trial of orbital atherectomy + BA vs. BA alone showed superiority with use of the orbital atherectomy device.⁷

Most trials comparing atherectomy + BA to BA alone were done without the use drug coated balloons. DCB's have shown superiority when compared to plain old balloon angioplasty alone. A recently published meta-analysis of 11 trials with 1838 patients confirmed that DCB's are superior with regards to endpoints such as primary vessel patency, restenosis rates and target lesion revascularization. The combination of both atherectomy with DCB may further improve the results of lower extremity PAD percutaneous intervention. Several trials are currently in progress that are evaluating this hypothesis. The Definitive AR trial is a randomized control trial comparing DAS+ DCB vs DCB alone. Long term data has yet to be published but preliminary results show that DAS+DCB may be superior especially in long as well as calcified lesions when appropriate de-bulking was attained (<30% residual post DAS stenosis).

Version 23JUL2020 Page 9 of 23

While both directional and orbital atherectomy systems have demonstrated improved outcomes versus balloon angioplasty alone, no studies have been performed to directly compare whether one form of atherectomy is superior to the other. With the increased incidence of significant PAD and the increased need for atherectomy in order to achieve successful percutaneous intervention, it would be extremely beneficial to know whether one type of atherectomy system is preferred over another. There are several theoretical advantages of DAS over OAS: DAS allows for possibly larger amount of plaque removal (de-bulking) which leads to a larger luminal gain and vessel diameter that in turn may lead to a better long term vessel patency rates and lower rates of target vessel revascularization. The purpose of this study will be to evaluate whether directional atherectomy is superior to orbital atherectomy in treating long femoro-popliteal lesions.

2.4 Study Objectives and Endpoints

2.4.a. Primary Objective

 To investigate the hard and soft plaque removal with directional and orbital atherectomy by analyzing changes in plaque volume and composition and vessel size using IVUS). Freedom from complications, target vessel patency and target lesion revascularization (TLR) at 6 months and one year will also be evaluated.

2.4.b. Primary Endpoint

Acute luminal gain (increase in minimal luminal area via IVUS measurement immediately following atherectomy)

2.4.c. Secondary Endpoints

- Plaque burden reduction. The plaque composition and amount of removed plaque will be analyzed via IVUS.
- Device success (≤ 30% residual stenosis following atherectomy, as measured by angiography, without adjunctive endovascular interventions)
- Rate of procedural angiographic complications such as dissection, perforation, emboli, abrupt closure, need for bail out stenting.
- Major Adverse Event Rate at 30 days post procedure defined as clinical TLR, major unplanned amputation of the treated limb, or all-cause mortality
- Rate of clinical TLR, unplanned amputation of the treated limb, or all-cause mortality at 6 and 12months post index treatment.
- Primary patency at 1 year defined as freedom from target lesion restenosis detected with duplex ultrasound Peak Systolic Velocity Ratio (PSVR) is ≤ 2.4
- Rate of Hemodynamic Improvement as assessed by changes in ABI at 6 and 12 months as compared to post-procedural baseline (i.e., within 30 days).
- Improvement in Rutherford Clinical Category within 30 days, at 6 months and at 12 months, defined as an improvement in clinical status indicated by a decrease of one or more in Rutherford Clinical Category compared to baseline, that is attributable to the treated limb (in cases of bilateral disease).

Version 23JUL2020 Page 10 of 23

3. Investigator Selection and Responsibilities

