5.1 Overview of Data Collection Requirements

Clinical data will be collected upon enrollment at the Baseline Visit, at the time of the procedure, and at within 30 days, and 6 and 12 months after the procedure. Data will also be collected during unscheduled office visits should adverse events connected to the procedure or device occur or should a subject death occur during the 12 months of study follow up after the subject's procedure. Data to be collected includes demographics, medical history, etc. The data requirements are summarized in Table 1.

Data Criteria	Baseline visit	Procedure	Visit 1	Visit 2 (6 mon)	Visit 3 (12 mon)
Compliance Window	30 days prior to procedure	n/a	Within 30 days after procedur e	+/- 30 days	+/- 30 days
Subject Informed Consent	✓				
Inclusion/Exclusion Criteria	✓				
Subject Medical History	✓				
IVUS/DICOM images*		✓			
ABI	✓		✓	✓	✓
Arterial Duplex Ultrasound			✓		√
Rutherford	✓		✓	✓	✓

Version 23JUL2020 Page 13 of 23

Follow-up Visit Form			✓	✓	✓
Adverse Event Form					
Deviation Form	As they occur				
*IVUS/DICOM images to be collected immediately prior to and immediately following use of the OAS/Hawkone and again following Drug Coated Balloon Angioplasty procedures.					

Table 1 Study Data Collection

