The ruler must be utilized for each procedure for precise measurement of the diseased, treated, and IVUS evaluated segment(s).

The Opticross[™] 18 peripheral imaging catheter (Boston Scientific Corp) is a 6-French (Fr) compatible catheter that performs intravascular analysis of the culprit lesion, measuring grey-scale images over a 0.014″ guidewire. This device is used routinely at the study center.

- 1. Automated pullback (1.0 mm/sec) must be implemented by using the disposable pullback device.
- 2. All pullbacks must be performed at a sufficiently distal point using an external ruler to mark the precise start point.
- 3. Images should be recorded on DICOM format and archived on DVD for off-line analysis.

 Anonymized IVUS images and selected angiograms (pre-treatment view of stenosis, IVUS location and final post-treatment angiogram) will be sent to the Core Laboratory for evaluation.

Adverse Event Collection

Complete SAE collection and assessment

5.5 Follow up.

All randomized/enrolled subjects will be evaluated prior to discharge from the index procedure and continue follow up evaluation at 30 days, 6 months, and 12 months after the index procedure. Requirements of each follow-up evaluation are described below.

Visit 1. 30 days Follow up (within 30 days)

All enrolled subjects must be evaluated within 30 days after the index procedure. The following assessments must be performed during this visit.

- Rutherford Clinical Category Assessment
- ABI Measurements
- Serious Adverse Events collection and assessment
- Arterial Duplex Ultrasound
- Antiplatelet medications assessment

Visit 2. 6 month Follow up (182 days +/-30 days)

All enrolled subjects must be evaluated 6 months after the index procedure. The following assessments must be performed during 6 month office visit.

- Rutherford Clinical Category Assessment
- ABI Measurements
- Serious Adverse Events collection and assessment
- Antiplatelet medications assessment

Visit 3. 12 month Follow up (365 days +/-30 days)

All enrolled subjects must be evaluated 12 months after the index procedure. The following assessments must be performed during 12 month office visit.

- Rutherford Clinical Category Assessment
- ABI Measurements
- Serious Adverse Events collection and assessment
- Arterial Duplex Ultrasound
- Antiplatelet medications assessment

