5.6 Unscheduled Visits

An unscheduled follow-up is defined as an office or hospital visit or phone call to the clinic by the subject that is not required by the study protocol but is usually related to an event and occurs between the study baseline visit and 12 months after the procedure. If the subject has an unscheduled follow-up and:

- No serious adverse events noted during unscheduled visit no forms need to be completed
- Serious adverse event noted The Adverse Event CRF needs to be completed for each event

The subject will still be required to return for the next scheduled follow-up visit if the unscheduled visit is out of the compliance follow-up window.

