6.1 Adverse Events

The only Adverse Events (AE) that will be collected in the study are those events that meet the definition of serious injury, also called a serious adverse event (SAE), which is required for post market surveillance of medical devices by the FDA

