8.2 Statistical and Data Analysis Methods

The Biostatistician from NYULMC will perform the analysis in collaboration with the Principal Investigator. No interim analyses are planned.

Descriptive statistics will be generated to describe study findings (i.e. subject demographics, plaque volume, lumen volume, vessel size, etc.). The mean differences between pre-procedure and post-procedure measures will be analyzed using paired t-tests. The pre- and post-procedure changes in the primary and secondary outcomes will be compared between the two treatment arms by the Intention to treat (ITT) principle. Multivariable linear regressions will be used to compare the change between treatments adjusting for subject demographics and other covariates. A p-value of \leq 0.05 will be considered to indicate statistical significance.

Group sample sizes of 30 and 30 achieve 80% power to detect a difference of 0.7 standard deviation difference in the mean of the primary outcome between the two groups with a significance level 0.05.

IVUS DICOM Image Analysis

Anonymized IVUS Images and selected angiograms should be recorded on DICOM format and archived on DVD for off-line analysis.

Quantitative assessment of the treated segments will be performed using planimetry echoPlague software (Inedc, Mountain View, CA).

9. Data Safety Monitoring

Due to the fact that this is an investigator initiated trial there will be no external monitoring or auditing for this study. In this study, a Clinical Event Committee (CEC) or a Data Safety Monitoring Board (DSMB) will not be used. The Principal Investigator will conduct interim monitoring of any serious adverse event at the time of occurrence and annually to assure the continuing safety of participants, relevance of the study question, appropriateness of the study protocol compliance and integrity of the accumulating data. The PI in conjunction with NYU IRB will be responsible for monitoring the data and conducting safety reviews every12 months when annual re-approval is sought. During the review process, the PI and NYU IRB will evaluate whether the study should continue unchanged, require modification/amendment, or close to enrollment. This study will not have predefined stopping rules due to the fact that both devices are proven to be safe in multiple clinical trials and approved by FDA for routine clinical practice.

Version 23JUL2020 Page 20 of 23

10. Investigator Records and Reports

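### Primary patency at 1 year is defined by duplex alone, so a target lesion re-treated before the 12-month scan can count as primary patent

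*Combined protocol and SAP*

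**What the plan says.** Section 2.4.c lists "Primary patency at 1 year defined as freedom from target lesion restenosis detected with duplex ultrasound Peak Systolic Velocity Ratio (PSVR") and sets the limit at 2.4 or less. The Protocol Summary repeats this: "freedom from target lesion restenosis detected with duplex ultrasound Peak Systolic Velocity Ratio (PSVR"), same limit. Neither place mentions repeat revascularization. Clinical target lesion revascularization (TLR) appears separately in 2.4.c, inside composites with amputation and death at 30 days and at 6 and 12 months. Nothing links it to patency.

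Table 1 in section 5.1 marks "Arterial Duplex Ultrasound" at Visit 1 (within 30 days) and at Visit 3 only. Section 5.5 agrees: duplex is absent from the 6-month list and returns at "Visit 3. 12 month Follow up (365 days +/-30 days").

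Section 8.2 says that "changes in the primary and secondary outcomes will be compared between the two treatment arms by the Intention to treat (ITT) principle". It has no rule for a lesion re-treated before the 12-month scan, or for a missing scan.

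On data capture, section 5.6 states "No serious adverse events noted during unscheduled visit no forms need to be completed", and section 6.1 states "The only Adverse Events (AE) that will be collected in the study are those events that meet the definition of serious injury". The Protocol Summary and section 2.2, however, allow data to be collected at unscheduled visits that concern treatment of the femoro-popliteal disease, without requiring a serious adverse event (SAE).

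**The concern.** A lesion that has been re-treated has lost primary patency in the ordinary sense of the term, yet the written definition looks only at a duplex result. If the lesion fails between the two scheduled scans, is re-treated on symptoms or angiography, and looks open at month 12, an analyst who follows the text scores a failure as a success.

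This matters because section 2.3 argues that directional atherectomy "may lead to a better long term vessel patency rates and lower rates of target vessel revascularization". Under the written definition, re-treatment raises apparent patency, and does so most in the arm that needs more of it. The two parts of the expected advantage then work against each other: a higher revascularization rate in one arm flatters that arm's patency.

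**Working it through.** The plan states no figure for patency to reproduce. Its one design figure, 80% power with 30 per arm, concerns the primary outcome and plays no part here.

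**Step 1: length of the gap.** Visit 1 falls by day 30. The Visit 3 window opens at day 365 − 30 = 335. The gap without a scheduled duplex is at least 335 − 30 = 305 days.

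**Step 2: how the text scores a lesion re-treated in the gap, with 2.4 or less at month 12.**
- If only the 12-month scan counts, the lesion is patent.
- If any duplex up to 1 year counts, it fails only when an unscheduled duplex showed restenosis before the re-treatment. Otherwise it is patent.

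**Step 3: weight of one lesion.** With one target lesion per subject and 30 evaluable subjects in the arm, 1/30 = 3.3 points.

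**Step 4: size in one arm.** Overstatement = TLR rate × q × u, where
- q is the share of re-treated lesions at 2.4 or less at month 12, assumed 0.7 to 0.9;
- u is the share not already failed by an earlier duplex, assumed 0.5 to 1 (u = 1 if only the 12-month scan counts).

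The TLR rate is also an assumption; the documents give none. At 10%:
- u = 1: 0.10 × 0.7 to 0.10 × 0.9 = 7 to 9 points
- u = 0.5: 3.5 to 4.5 points

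The range is therefore 3.5 to 9 points.

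**Step 5: effect on the difference between arms.** Assume true primary patency of 90% v 80%, that is, failures of 10 and 20 points, with u = 1 and the same q in both arms.

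| Failures re-treated | q | Reported patency | Difference (true: 10) |
|---|---|---|---|
| All | 0.7 | 90 + 7 = 97 v 80 + 14 = 94 | 3 |
| All | 0.9 | 90 + 9 = 99 v 80 + 18 = 98 | 1 |
| Half | 0.7 | 90 + 3.5 = 93.5 v 80 + 7 = 87.0 | 6.5 |
| Half | 0.9 | 90 + 4.5 = 94.5 v 80 + 9 = 89.0 | 5.5 |

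**Step 6: the same effect in whole subjects.** Assume 4 restenoses without re-treatment in each arm, TLR in 2 v 6 subjects, q = 1 and u = 1. As written, both arms report 26/30 = 86.7%. With TLR counted as failure they report 24/30 = 80.0% v 20/30 = 66.7%.

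**The case against.** **The intent may already be there.** The word primary, and the phrasing as freedom from restenosis, may be meant to exclude re-treated lesions. That is plausible, but the protocol supplies its own definition and leaves the condition out. Even if the whole year counts, restenosis must still be seen on duplex, and none is scheduled in the gap.

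**Re-treatments remain visible.** This stands in part. Clinical TLR is an endpoint in its own right, so the trial has to record it, and the objective names TLR at 6 months and one year. A reader might infer from sections 5.6 and 6.1 that re-treatments go uncollected. The documents do not support that: the Protocol Summary and section 2.2 permit collection at such visits, and the Follow-up Visit Form may ask for it, though its content is not described. What remains is a tension between a permissive statement and a rule that no form is needed without an SAE. In addition, 2.4.c places TLR inside composites, so a reader could not reliably correct the patency rate from them.

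**The between-arm comparison of patency is not clearly specified.** This is fair. The sentence in section 8.2 concerns pre- to post-procedure changes, and patency has no pre-procedure value. The scoring error enters each arm's rate all the same, and so any contrast drawn between the arms.

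**The magnitude is assumed.** It is. A reader might take the shrinkage from 10 points to 1–3 as the expected effect, but it requires every failure to be re-treated. A reader might also infer a spurious significant difference arising from different re-treatment practice. Nothing in the documents suggests that practice differs by arm, and with 30 per arm the harm is to the estimate rather than to the error rate.

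**Conclusion.** The point holds as a gap in the definition. Read as written, a target lesion re-treated between day 30 and the 12-month scan, with a ratio of 2.4 or less at that scan, can be scored primary patent. The exception is a lesion whose restenosis was shown on an earlier unscheduled duplex that is counted.

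The missing condition and the 305-day gap are certain from the text. The size is not known. On the assumed inputs, 10% TLR overstates an arm's patency by 3.5 to 9 points. A true 10-point difference would be reported as 1 to 3 points if all failures are re-treated, or 5.5 to 6.5 points if half are (both at u = 1).

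The consequence is limited to one unpowered secondary endpoint. The primary IVUS endpoint and its power statement are unaffected. It should still be fixed, because the protocol offers patency as part of the rationale for the comparison and the correction is cheap.

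**What to change.** In section 2.4.c and the Protocol Summary, replace the definition with:

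> Primary patency at 1 year = PSVR ≤ 2.4 on the 12-month duplex AND no target lesion revascularization (endovascular or surgical) before that duplex or, if no 12-month duplex was done, before the close of the 12-month window (day 395). Any such revascularization counts as loss of primary patency.

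Day 395 is 365 + 30. Without it, subjects who have no 12-month scan would have no cut-off date.

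Also:
- State how amputation of the treated limb is scored for patency.
- Report subjects with neither a revascularization nor a 12-month duplex as not evaluable, with counts by arm.
- Add a best/worst-case sensitivity analysis that counts the non-evaluable subjects all as patent, then all as failed. It is needed because the rule fails re-treated subjects who are unscanned but leaves out other unscanned subjects. Illustration with assumed counts for an arm of 30 (24 scanned, of whom 20 are patent; 3 re-treated and unscanned; 3 other unscanned): the main result is 20/27 = 74.1%, with a range from 20/30 = 66.7% to 23/30 = 76.7%.
- Reconcile the statement in the Protocol Summary and section 2.2 on unscheduled visits with section 5.6, so that the date of every target lesion revascularization is recorded whether or not it is an SAE.

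The cost is a few wording edits and, if the form lacks it, one dated field. No visit or scan is added. Reported patency will be somewhat less favourable, by the share of re-treated lesions that would otherwise have scored patent.
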